3.11 Assessments at Each Visit

Visit 0 – Day 0 - Screening / Baseline / Randomization Visit

Before any screening procedures take place, potential subjects will be provided with written and oral information about the study and the procedures involved. They will be fully informed about their responsibilities and of all the procedures involved in the study, the possible risks with the study product and their rights while participating in the study. They will have the opportunity to ask questions and time to consider participation. If the subjects wish to participate in the study, they will be asked to sign and date an Informed Consent Form. The form must be signed and dated by the subjects as well as by the person who conducted the informed consent procedure before any study-related activities are performed.

Subjects will be warned to come to study centre (for all the Visits: V0, V1 and V2):

- \geq 12 hours overnight fast
- Avoid caffeine for 72h before
- Avoid high-fat food the day before
- Avoid tobacco for at least 4-6h before
- Abstain from exercise for >12h before

All subjects will have a screening evaluation that includes the following:

- Signature on Informed Consent Form
- Check eligibility criteria
- Medical history and demography
- Concomitant medication monitoring and recording
- Brief physical examination
- Measuring weight and height (BMI calculated)

If they will be deemed eligible the randomization process will take place, i.e. each subject will be assigned a number according to the order of inclusion in the study; the following procedures will take place:

- Explanation of dietary restrictions (to be followed for the whole study)
- Randomisation: subjects will be assigned a number according to order of inclusion in the study
- Blood sample collection for laboratory parameters (triglycerides, glucose, C-reactive protein – CRP, LDL Cholesterol - to be checked for inclusion criteria), red / ox CoQ10 levels evaluation and assessment of the levels of the markers of oxidative stress
- Acclimatisation
- Vital signs (blood pressure)
- FMD measurement
- Supply products (according to randomization) for consumption at home
- Supply of daily diary

Until the following visit the subjects will be instructed to consume the study product at home and to complete the daily diary. Diary and unopened and empty study products packs will be returned as an assessment of compliance. The following visit will be scheduled after 4 weeks.

Visit 1 - Week 4

During this visit the following activities will have to be performed:

- Confirmation of eligibility criteria
- Compliance check (fasted, dietary restriction and diary check)
- Concomitant medication / adverse events monitoring and recording
- Blood sample collection for laboratory parameters (triglycerides, glucose, C-reactive protein – CRP, LDL Cholesterol - to be checked for inclusion criteria), red / ox CoQ10 levels evaluation and assessment of the levels of the markers of oxidative stress
- Brief physical examination
- Acclimatisation
- Vital signs (blood pressure)
- FMD measurement
- Supply products (according to randomization) for consumption at home
- Supply of a new daily diary
- Collection of the completed daily diary and unopened and empty product packs

Diary and unopened and empty study products packs will be returned as an assessment of compliance. The following visit will be scheduled after 4 weeks.

Visit 2 – Week 8 – End of Study Visit

During this visit the following activities should be performed:

- Compliance check (fasted, dietary restriction and diary check)
- Concomitant medication / adverse events monitoring and recording
- Blood sample collection for laboratory parameters (triglycerides, glucose, C-reactive protein – CRP, LDL Cholesterol - to be checked for inclusion criteria), red / ox CoQ10 levels evaluation and assessment of the levels of the markers of oxidative stress
- Brief physical examination
- Acclimatisation
- Vital signs (blood pressure)
- FMD measurement
- Collection of the completed daily diary and unopened and empty product packs

Table 1. Study flow chart

Visits	V0 Screening visit /Baseline/ Randomization visit	V1	V2 End of Study visit
Week (+/- 2 days)	0	4	8
Informed Consent	x		
Inclusion/Exclusion Criteria	x	x	
Medical history	x		
Demography	x		
Concomitant medication	x	x	x
Physical examination	x	x	x
Randomization	x		
Blood sample	x	x	x
FMD	x	x	x
Study product supply	x	x	
Study product return		x	x
Diary supply	x	x	
Diary return		x	x
AE/SAE evaluation		x	x

4. Study Products

The active study products, Ubiquinol-QH 100 mg, will be provided in the form of softgel capsules.

Each active softgel capsule contains ubiquinol (Kaneka QH™ active antioxidant form of coenzyme Q10) 100 mg.

The product contains also soy and other ingredients: medium chain triglycerides, gelatin, glycerin, ascorbyl palmitate, purified water, beeswax, soy lecithin, annatto extract.

Placebo will consist of softgel capsules too, matching the active study products but without any active principle.

The subjects will consume 2 softgel capsules according to the following scheme:

	Number of soft capsules/day	
	Ubiquinol-QH 100 mg	Placebo
Group A: Ubiquinol 200mg/day	2	0
Group B Ubiquinol 100mg/day	1	1
Group C: Matched placebo	0	2

4.1 Presentation and Administration

The study products, provided as softgel capsules, will be consumed at home by the subjects in the morning and in the evening, with a meal.

4.2 Storage

The study products will be stored in the pharmacy of I.N.R.C.A., Ancona; dose packets will be handed over at the study site by the PI or his/her designee.

4.3 Accountability

The accountability of the study products will be regularly checked and a person from the medical staff will maintain the accounts of study products in the study product log.

4.4 Breaking the Code in an Emergency

Subjects and site personnel will be blinded with regard to the identification of specific treatments.

A randomization schedule will be generated. The Pharmacy custodian / designate independent of the study will conduct the dispensing procedure.

The link between the treatment code and the treatment will not be available to the personnel involved in the collection, revision, or evaluation of adverse events, to the clinical laboratory, or to personnel who could have an impact on the outcome of the study, until after the end of the study (when all adverse events have been finalized) and analytical phases.

After the study, blind review meeting will be organized with soft data between PI and Statistician; decision on breaking of code will be taken only after the blind review team decides to hard lock the data.

5. Safety Monitoring

5.1 Adverse Event

An adverse event (AE) is any untoward medical occurrence in a subject, whether or not related to study product or study procedures. Adverse events include any occurrence that is new in onset, an exacerbation of a pre-existing condition and clinically significant laboratory values.

5.1.2 Study Specific Expected Adverse Event

While trained and experienced nurses/phlebotomists will draw the blood with utmost care, there is a possibility that some of the subjects may experience haematoma (bruise or collection of blood under the skin with minor swelling in the area, which may last for few days), fainting or injury to the nerves after venipuncture. Moreover, temporary occlusion of arm during FMD measurement may cause transient hematoma, discomfort or paresthesia. These symptoms will not be recorded as adverse events.

Rarely, ubiquinol may cause mild gastrointestinal upset, decrease in appetite, nausea, vomiting, diarrhea or constipation and rash.

5.2 Serious Adverse Event

A serious adverse event (SAE) is an AE that results in any of the following outcomes: death; a life-threatening event; in-patient hospitalization; prolongation of existing hospitalization; a persistent or significant disability/incapacity; a congenital anomaly or birth defect. Any other important medical event may be considered a SAE when the event may jeopardize the subject and may require medical or surgical intervention to prevent one of the outcomes listed previously. Examples of such medical events include allergic bronchospasm requiring intensive treatment in an emergency room or at home, or convulsions that do not result in in-patient hospitalization. Just as a stable pre-existing condition is not an AE, hospitalisation for elective treatment (e.g. cosmetic or dental procedure) of a pre-existing condition that did not worsen from baseline is not an SAE.

5.3 Severity and Relatedness of Adverse Events

An AE will be recorded only once, with the most extreme severity. Severities are defined as:

Mild	Awareness of symptoms which require minimal or no treatment and do not interfere with daily activity
Moderate	Discomfort or low level of interference which is enough to interfere with but not prevent daily activity
Severe	Interrupted or unable to perform usual daily activity and usually requires treatment.

The likelihood that the AE was related to the study product or study procedure is defined as;

Not Related	The AE is clearly due to an alternative cause, even if this cannot be definitely identified. Alternative causes include disease or environmental factors.
Unlikely	A connection between the AE and the study product or procedure is unlikely. 
• The AE has a relationship in time to the study product or procedure• An alternative cause (e.g. disease or environmental factors) is the most likely explanation, even if this cannot be identified.
Possibly	A connection between the AE and the study product or procedure cannot be ruled out with certainty. 
• The AE has a relationship in time to the study product or procedure

	
 • An alternative cause (e.g. disease or environmental factors) seems likely or possible or there is significant uncertainty about the cause of the AE.
Probably	
There is a high degree of certainty that the AE is related to the study product or procedure.
 
 • The AE has a relationship in time to the study product or procedure • A possible alternative cause may be present. • AE disappears or decreases on withdrawal or reduction of study product or procedure (if performed).
Definitely	
The AE is clearly related to the study product or procedure.
 
 • There is a strong relationship in time • An alternative cause is unlikely • AE disappears or decreases on withdrawal or reduction of study product or procedure (if performed)

5.4 Reporting of Adverse Events

All AEs will be recorded in the CRF. All AEs will be coded using ICD-9 and reported according to local regulations.

It should also be remembered that, referring to the legislation currently in force, doctors are obliged to notify any suspected adverse reaction of which they become aware in their clinical practice, by completing the appropriate specific reporting form.

Once completed, this form will be sent to the Pharmacovigilance team responsible for the relevant health institution the Investigator belongs to.

5.5 Follow-up of Adverse Events

The PI or designee will ensure that adequate medical care (if required) is provided to a subject for any study related AE. If an AE is ongoing at the end of the study, follow-up visits will be performed until the AE has resolved or stabilised or the PI determines that no further follow up is necessary. Follow-up visits may take the form of subject visits, a referral to another specialist, site telephone calls to the subject or letters from the treating physician.

The PI or designee must comply with the specific reporting requirement(s) of the ethics committee.

6. Statistical Considerations

6.1 Sample Size Calculation

Sample size calculation is carried out with use of G*power Software.

The parameters used to compute sample size for this study were taken from the reference article by Gao et al 2012, a meta-analysis of 5 randomized controlled trials.

Mean and SD taken from the article by Watts GF et al 2002, one of the RCT mentioned in reference article (see fig. 2 in the article by Gao et al), were considered as appropriate values to be taken into account: considering group one mean and SD as 1.6 (1.16) and second group mean and SD as -0.4 (2.24), with 80% power and 5% two-sided significance level, 14 subjects are required for one group.

In this study, considering a 20% dropout rate, a total of 52.5 subjects should have been enrolled; a sample size equal to 51 subjects was deemed as appropriate.

It is to be noted that in this study the minimum increment of FMD reached with the number of patients provided for each group is to be considered as equal to 1.6% (according to Figure 2 shown in Gao et al, in particular by referring to the study of Watts, which provides a sample size similar to ours).

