1.2 Rationale for Study

Coenzyme Q10 (CoQ10, also known as ubiquinone -10) is a powerful lipophilic physiological antioxidant; it is part of the mammal mitochondrial electron transport chain and plays an important role in cellular respiration and ATP production. CoQ10 exists in an oxidized form (ubiquinone) that must be converted into the biologically-active, reduced form (ubiquinol) before being utilized. CoQ10 is naturally synthesized by the body and can be obtained in an oxidized or mixed form from the diet in foods such as corn, nuts, soy, broccoli, meat and fish. Oral supplementation of CoQ10 is able to increase CoQ10 levels in plasma, white blood cells and platelets. Supplementation with CoQ10 has been shown to positively affect heart performance in congestive heart failure and ischemic heart disease, and has been shown to have a clinically significant blood pressure lowering effect (Gao et al 2012).

The effect of oral CoQ10 supplementation on endothelial function has been studied in randomized controlled trials focused on the effect of CoQ10 supplementation on endothelial function as measured by FMD of the brachial artery (Gao et al 2012).

In the systematic review and meta-analysis by Gao et al 2012, evidence published from 5 randomized, double-blind, placebo controlled clinical trials that investigated the effect of CoQ10 therapy on endothelial function as measured by FMD, were summarized. It was found that CoQ10 therapy substantially enhances FMD. The absolute increase in FMD of 1.70% after CoQ10 supplementation is of clinical significance, as an absolute improvement in FMD of 1% may already translate into a 10–25% reduction in residual cardiovascular risk for these patients (Neunteufl et al 2000; Shimbo D et al 2007).

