In this study the minimum increment of FMD reached with the number of patients provided for each group is to be considered as equal to 1.6% (according to Figure 2 shown in Gao et al, in particular by referring to the study of Watts, which provides a sample size similar to ours). It was shown that CoQ10 possess the capability of enhancing endothelial functionality by counteracting nitric oxide oxidation (Tiano L et al 2007). Moreover, CoQ10 supplementation is able to improve endothelial dysfunction in statin treated type 2 diabetic patients, possibly by altering local vascular oxidative stress [Hamilton SJ et al 2009] and also to improve endothelial function of conduit arteries of the peripheral circulation in dyslipidemic patients with type 2 diabetes perhaps increasing endothelial release and / or activity of NO due to improvement in vascular oxidative stress (Watts GF et al 2002)

In patients with ischaemic left ventricular systolic dysfunction (LVSD), 8 weeks supplement of CoQ improved mitochondrial function and FMD: in particular the improvement of FMD correlated with the change in mitochondrial function, suggesting that CoQ improved endothelial function via reversal of mitochondrial dysfunction in patients with ischaemic LVSD (Dai YL et al 2011).

Supplementation with either ubiquinol or ubiquinone increases ubiquinol levels in plasma lipoproteins and the heart and thereby enhances resistance of LDL (Low Density Lipoprotein) to free radical oxidation and cardiac ATP (Adenosine triphosphate) production. The higher bioavailability and biological activity of ubiquinol however, increases its beneficial effects (Cohen MM 2015). This was demonstrated in a cross-over trial that involved 4 weeks of supplementation with either 200mg/day of ubiquinol or ubiquinone. While both forms significantly increased total plasma CoQ10 the increase with ubiquinol was nearly twice that produced by ubiquinone. This study also found that plasma ubiquinol/total CoQ10 ratio increased significantly from baseline during ubiquinol supplementation, yet remained unchanged after ubiquinone supplementation [Langsjoen PH and Langsjoen AM 2014]. However, only recently ubiquinol become available as a supplemental nutrient.

This study will be conducted to understand the effects of a supplementation of ubiquinol (200 mg / 100 mg daily) on FMD in male and female subjects at risk of cardiovascular disease development.

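### The 1.6% given as the minimum FMD increment for the planned group size is the assumed active-arm mean; the difference from placebo that the calculation powers is 2.0

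*Protocol*

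**What the plan says.** Protocol section 6.1 takes its inputs from one trial in a published meta-analysis: "considering group one mean and SD as 1.6 (1.16) and second group mean and SD as -0.4 (2.24"). From these it concludes that "with 80% power and 5% two-sided significance level, 14 subjects are required for one group". It then allows for 20% drop-out, arrives at 52.5 subjects and settles on 51, which section 3.3.1 gives as 17 per group.

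The last paragraph of 6.1 adds that "the minimum increment of FMD reached with the number of patients provided for each group is to be considered as equal to 1.6" percent, and refers to the same source trial because its sample size is similar. Section 1.2 repeats the statement: "minimum increment of FMD reached with the number of patients provided for each group is to be considered as equal to 1.6" percent.

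The primary endpoint (section 2) is the week 8 change in FMD, with both ubiquinol groups compared with placebo. Section 1.2 also cites a pooled result: "The absolute increase in FMD of 1.70% after CoQ10 supplementation is of clinical significance".

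**The concern.** A minimum effect that is tied to the number of patients per group reads as the sensitivity of the design. Because the primary comparison is against placebo, a reader will tend to take 1.6 points as the smallest difference from placebo that the trial is sized to show. The sample size was not computed for 1.6. It was computed for 2.0, and 1.6 is one of the two means that produce that difference.

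What is at stake is how the trial's sensitivity is understood. Someone who relies on the sentence would believe that effects of 1.6-1.7 points are covered at the planned power. At the planned drop-out, a single dose-placebo comparison would miss a true difference of that size about one time in three or somewhat more often.

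**Working it through.** **Inputs (section 6.1 unless noted).** Active mean 1.6, SD 1.16; comparator mean -0.4, SD 2.24; 80% power; two-sided 5%; 14 per group; 20% drop-out; 17 enrolled per group (section 3.3.1). All figures are for one dose-placebo comparison, with no adjustment for there being two.

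**Step 1: the difference that was powered.**

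- Difference = 1.6 - (-0.4) = 2.0
- Common SD = √((1.16² + 2.24²)/2) = 1.784
- Standardised difference d = 2.0/1.784 = 1.121

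**Step 2: reproduce the 14 per group.** For a two-sample t test with n per group, power comes from the noncentral t distribution with 2n - 2 degrees of freedom and noncentrality δ/(SD·√(2/n)). With δ = 2.0:

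- n = 13: 78.3%
- n = 14: 81.5% (80.5% with a Welch test)

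So 14 is the smallest n that reaches 80%, and the plan's figure reproduces. The drop-out step also reproduces: 3 × 14/0.8 = 52.5. With 51 enrolled, 17 × 0.8 = 13.6 are expected to be evaluable per group.

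**Step 3: power at the differences the protocol mentions** (same SD, same formula).

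| Difference from placebo | 13.6 per group | 14 per group | 17 per group (no drop-out) |
|---|---|---|---|
| 2.0 (used in 6.1) | 80.3% | 81.5% | 88.7% |
| 1.70 (pooled effect, 1.2) | 66.6% | 68.0% | 76.9% |
| 1.6 (stated minimum) | 61.4% | 62.7% | 71.8% |

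The Welch test gives 61.6% for a difference of 1.6 at n = 14 and 70.9% at n = 17. Reaching 80% power at 1.6 takes 21 evaluable per group.

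**Step 4: what would a minimum for this group size be?** Solving the same formula for the difference that gives 80% power:

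- 13.6 per group: 1.99
- 14 per group: 1.96
- 17 per group: 1.77

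The other usual meaning is the smallest observed difference that reaches p < 0.05, which is t(0.975, 2n - 2)·SD·√(2/n). This gives 1.39 at n = 14 and 1.25 at n = 17.

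The value 1.6 matches none of these. It does match the group-one mean exactly.

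**The case against.** The strongest reply is that the sentence never mentions a detectable difference or placebo. An increment of FMD is naturally a change from baseline, the figure equals the active-arm mean given in the same section, and it is credited to the same trial. On that reading, an active-arm rise of 1.6 with placebo at -0.4 is the 2.0 scenario, and 80% power is right. This stands in part: the wording allows the active-arm reading, and that is probably where the number came from. It does not rescue the sentence. On that reading 1.6 is an assumed mean, not a minimum, and it corresponds to the powered difference only if placebo falls by 0.4, which the sentence does not say. If placebo does not change, an active-arm rise of 1.6 is a difference of 1.6.

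A reader might go further and infer that the protocol claims 80% power for 1.6 and is contradicted by its own figures. The text does not support that. It attaches 80% only to 1.6 versus -0.4, where it is correct, and states no power for a difference of 1.6. There is no arithmetic error in the 14 or the 52.5.

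It is also fair that the number provided per group is 17, so 61-63% applies only after the planned drop-out. If all 17 are evaluable, power for 1.6 is about 72%, still below 80%.

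Two further inferences should be kept out of this point. One is that 2.0 was the wrong planning effect, because it exceeds the pooled 1.70 and comes from patients with type 2 diabetes. That is a judgement on the choice of assumption, and section 6.1 discloses the source. The other is that the protocol must say how a null result will be reported. That is commonly left to the statistical analysis plan, which is not at hand.

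**Conclusion.** The point holds as a misstated sensitivity figure, of moderate weight. Sections 6.1 and 1.2 present 1.6% as the minimum reached with the planned group size. It is the active-arm mean carried over from the source trial. The design has 80% power for a difference from placebo of about 2.0 points at 14 evaluable per group, or about 1.8 with no drop-out. If 1.6 is meant as a difference from placebo, power falls short of 80% by about 17-19 percentage points at 13.6-14 evaluable (80 - 62.7 = 17.3; 80 - 61.4 = 18.6) and by about 8 at 17 (80 - 71.8 = 8.2).

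These figures assume the SDs in section 6.1 combined to 1.784, a two-sided 5% t test, and a single comparison with placebo. Adjusting for two comparisons would lower the power further. The sample size itself, and the 80% stated for a difference of 2.0, are not in question.

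**What to change.** In sections 6.1 and 1.2, replace the 1.6% sentence with:

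> With about 14 evaluable subjects per group the study has 80% power for a between-group difference in FMD change of about 2.0 percentage points (about 1.8 if all 17 per group are evaluable), in a single two-sided 5% comparison with placebo. Power for a difference of 1.6 is about 62% (72% with 17). The 1.6 is the assumed change in the active arm, with -0.4 assumed under placebo.

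The cost is wording in two places and a less favourable stated sensitivity. Enrolment, endpoint and allocation do not change.
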